**SAMPLE SIZE CALCULATION (Power 0.8, Alpha 0.05)**

- Probability of event in Group A: 0.20
- Probability of event in Group B: 0.07
- Proportion of sample in Group A: 0.50
- Evaluable subjects needed in Group A: 123
- Drop-out: 0.18

**N = 300**

*Estimation of drop-out rate:*

- A 10% loss at follow-up or death at 3 months is expected in this elderly patient population.
- In approx. 8% of cases, an inconclusive cardiac 4DCT can be expected.

## **9. PARTICIPATING CENTERS**

The GALILEO-4D trial is a multicenter, open-label, randomized, active-controlled trial and will be conducted as a substudy of the international GALILEO trial. Some selected centers participating at the GALILEO trial – and having the possibility to perform cardiac 4DCT-scans – will be offered the possibility to include patients in the GALILEO-4D trial. Inclusion will be by competitive enrollment until inclusion of 150 patients in both treatment groups of the GALILEO-4D trial

**Coordinating center:** Rigshospitalet - University Hospital, Copenhagen, Denmark

## **10. CLINICALTRIALS.GOV AND DATATILSYNET**

The GALILEO-4D trial will be registered at ClinicalTrials.Gov and will be conducted according to guidelines of the Danish Datatilsynet (Danish Data Protection Agency – The act implements the European Directive 95/46/EC on the protection of individuals with regard to the processing of personal data and on the free movement of such data). The study results will be published regardless of the outcomes and conclusions that can be extracted.

## **11. ECONOMICS**

The study is being economically supported by Bayer AG (Germany) to cover study costs – this financial support will be used primarily for research staff as well as for financial compensation of participating centers for additional study costs (such as 4DCT scan, echocardiography). None of the study investigators or members of Study Committees has a financial interest in the study. None of the supporters will have any conflict of interest with regard to the results of the study. Insurance and any legal requirements of the trial follow local legislation.

## 12. ETHICAL ASPECTS

There are some ethical issues involved in the treatment and follow-up part of this study. Anti-coagulation treatment in TAVR patients has proven to be safe in previous studies and in our experience with TAVR patients with previously known AF. There might be a slightly increased bleeding risk, however, this bleeding risk is kept to a minimum due to the exclusion of patients with an *a priori* increased bleeding risk (see exclusion criteria). We can consider this risk well counterbalanced by the advantage of reducing the risk of reduced valve leaflet motion as well as the risk of stroke. The risk related to the 4DCT-scan is low – patients with a renal insufficiency, iodine contrast allergy and/or contraindications for CT are excluded (see exclusion criteria) Concerning the radiation dose of the 4DCT-scan, we can report that patients will receive a radiation dose of 5-20mSievert, depending on weight and heart frequency/rhythm. It can be calculated that lifetime risk to die from cancer, hereby, theoretically increases with maximally 0,06%. Thus, the patients' lifetime risk to die from cancer increases from 25,0% to 25,06%. Furthermore, more than 95% of all study patients are expected to be more than 70 years of age. The patients are informed orally and in writing and are only included in case of written consent. Results of the study are expected to be of value for future patients undergoing TAVR.

## 14. 4DCT-SCAN – TECHNICAL REQUIREMENTS & PROTOCOL

### 4DCT-scan – technical requirements

It is essential to have optimal CT image quality for accurate assessment of TAVR leaflet morphology and motion. The highest degree of image quality is needed especially during the systolic phase of the cardiac cycle, whereas late-diastolic images are less important. High performance in terms of temporal and spatial resolution of the CT technology used is mandatory. Each participating site are requested to forward pilot data-sets to the Corelab at Rigshospitalet for image quality assessment, prior to study initiation. Accordingly, a list of minimal requirements in terms of CT methodology is tabulated below.

**MDCT scanner type:** High-end CT scanners with >64 detector technology are required. Any CT vendor will be allowed, provided that the site has comprehensive experience in cardiac CT imaging using the specific CT tomograph. Each site is requested to specify CT-scanner type and number of performed ECG-gated cardiac CT scans yearly.

**Patient preparation pre-MDCT:** To achieve the highest possible temporal resolution and hemodynamic standardization of valve function - regardless of CT scanner used – all patients will be required to undergo pre-treatment with betablocker or ivabradine for heart-rate control. Target heart rate is less than 65 bpm. Each site is requested to specify if heart-rate control is part of the current routine of the CT unit.

**MDCT-contrast:** Contrast injection system (single vs dual-phase) and contrast type are according to local preference. Each site is requested to specify injection protocol and contrast type routinely used.

**MDCT-acquisition:** Arterial phase (LV or descending aortic triggering), retrospective image acquisition with recordings of the entire R-R interval is needed. Both dose-modulation, reducing dose during diastole or without dose-modulation is allowed. Scan-field of view (Z-axis) should be 1 cm above and 1 cm below the TAVR stent frame. In centers, where radiation dose and scanner specifications allow it, a Z-axis 1 cm above the TAVR stent frame and below the caudal boundary of the left ventricle should be recorded. Vendor specific scan protocols will be provided to each individual site. In addition to scan parameters, heart rate and blood pressure during the scan should be recorded.

**MDCT-reconstruction:** Recorded image data should be reconstructed using appropriate filtering and iterative reconstruction according to a vendor specific protocol provided. Data sets of lowest possible slice thickness (0.5-0.9 mm) at each 5% intervals of the R-R cycle (0-95%) should be reconstructed including the TAVR. In addition, at site where the whole heart may be included in the image, data sets of 2 mm slice thickness at each 5% interval of the R-R cycle should be reconstructed including the heart chambers. These images will be used to assess LV cardiac volumes and specifically LV stroke volume.

**MDCT-images:** All recorded MDCT image data should be saved in DICOM format and forwarded to the Corelab at Rigshospitalet.

## 4DCT-scan – protocol

**Scan protocol:** Prior to imaging, patients are required to abstain from caffeine intake 16 hours before the scan. Baseline ECG, heart rate and blood pressure are recorded and reviewed before the scan. A single dosage of oral metoprolol (50 to 150 mg) is administered 1.5-2 hours before the scan, according to the heart rate, blood pressure and weight. In patients with a heart rate more than 60 bpm at the time of CT scan, additional metoprolol i.v. should be given for heart rate control. In patients with metoprolol contraindications (allergic asthma or left ventricular ejection fraction below 30%) a single dose of oral ivabradin (15 mg) is given 2 hours prior to the scan.

Patients should be scanned using a 320-row multidetector CT (MDCT) scanner, using a dedicated 4D CT volume image protocol. An image noise standard deviation level of 30 is predefined, which results in a variable kV and mA per patient. The kV is set to 120 by default; if this results in a maximal mA the kV is raised, until a sub-maximal mA is reached. The start- and end-position of the scan is determined by the initial scanogram. Start-position is defined as 20 mm cranial to the metal stent frame of the valve and end-position 16 mm (maximal Z-axis coverage) caudally by retro-spective volume imaging. To minimize radiation exposure, a dose-modulation approach can be used, reducing dose in the 55-100% RR-range (diastole). The contrast images are recorded by one rotation of the gantry at a heart rate of less than 75 bpm, by two rotations at a heart rate of 75 to 100 bpm, and by three rotations at a heart rate above 100 bpm. A total volume of 70-110 ml contrast agent (Visipaque, GE Healthcare) – depending on the weight of the patient – is infused at a rate of 5-6 ml/sec. The scans are initiated by real time bolus tracking in the left ventricle. Images are reconstructed at 0.5 mm slices with 0.25 mm overlap with an FC03 filter and an iterative reconstruction algorithm (AIDR) for valve evaluation at 5% intervals within the 0-95% RR range.

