#### ➤ Exclusion criteria

1. Severe renal insufficiency (eGFR < 30 ml/min/1.73 m^2) or on dialysis, or post-TAVR unresolved acute kidney injury with renal dysfunction ≥ stage 2
2. Iodinate contrast media allergy or other conditions that prohibit CT imaging (i.e. multiple myeloma, etc.)

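### Section 14 requires a rate-lowering drug before every research scan and leaves no option to withhold it, even with a low heart rate, low blood pressure or high-grade AV block

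*Combined protocol and SAP*

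**What the plan says.** Two parts of Section 14 govern pre-treatment.

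- **Technical requirements, patient preparation.** The rule is universal: "all patients will be required to undergo pre-treatment with betablocker or ivabradine for heart-rate control". The reasons given are temporal resolution and "hemodynamic standardization of valve function". The target heart rate is below 65 bpm.
- **Scan protocol.** ECG, heart rate and blood pressure are recorded and reviewed before the scan. Then: "A single dosage of oral metoprolol (50 to 150 mg) is administered 1.5-2 hours before the scan, according to the heart rate, blood pressure". The dose also depends on the patient's weight. If the rate is above 60 bpm at the scan, "additional metoprolol i.v. should be given for heart rate control". For patients who should not have metoprolol: "In patients with metoprolol contraindications (allergic asthma or left ventricular ejection fraction below 30%) a single dose of oral ivabradin (15 mg) is given".

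The substudy exclusions in Section 5.1 cover severe renal impairment or unresolved kidney injury, and "Iodinate contrast media allergy or other conditions that prohibit CT imaging". They do not mention slow heart rate, low blood pressure or conduction disease. Section 6.3 keeps the scan result from the treating physician and the patient until the main trial ends. The one exception is an additional scan after a thromboembolic event.

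**The concern.** The plan itself treats heart rate, blood pressure and the ECG as relevant to giving these drugs, since it has all three reviewed first. Yet no finding on that review leads to giving no drug. A site that follows the text exactly would give at least 50 mg of metoprolol, or 15 mg of ivabradine, to a patient with a resting rate of 50 bpm, a low systolic pressure or high-grade AV block.

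What is at stake is participant safety. Section 12 expects more than 95% of patients to be over 70, and all have recently had TAVR. The drug is given only to improve a research image whose result the patient does not receive, so there is no direct benefit to set against an avoidable reaction. Section 12 discusses the scan's risk in terms of renal function, contrast allergy, CT contraindications and radiation, and does not mention the rate-lowering drugs.

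**Working it through.** The plan gives no figure on this point to reproduce. The check is to follow the written rule for each kind of patient and see whether any path ends without drug.

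**Inputs (Section 14):** pre-treatment for all; target below 65 bpm; oral metoprolol 50 to 150 mg; i.v. metoprolol above 60 bpm at the scan; contraindications allergic asthma and LVEF under 30%; ivabradine fixed at 15 mg.

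| Patient on the scan day | Path in the text | Least drug given |
|---|---|---|
| Rate 50 bpm, no listed contraindication | Target already met; metoprolol scaled down | 50 mg metoprolol |
| Low blood pressure, no listed contraindication | Metoprolol scaled down | 50 mg metoprolol |
| High-grade AV block, no listed contraindication | Not on the contraindication list | 50 mg metoprolol |
| The same patient, if the site treats AV block as a contraindication | Switch | 15 mg ivabradine |
| Asthma or LVEF under 30%, at any rate or pressure | Switch; dose not scaled | 15 mg ivabradine |
| Above 60 bpm at the scan, at any pressure | i.v. top-up with no pressure or ECG condition | Oral dose plus i.v. metoprolol |

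No row ends without drug. Scaling lowers the metoprolol dose to 50 mg at least, and it does not apply to ivabradine. Reading the bracketed contraindications as examples only does not help, because the consequence is still ivabradine.

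**How many patients the rule covers.** Section 8 expects 10% loss or death by three months: 300 × (1 − 0.10) = 270 patients reach the scan, and all must be pre-treated. The documents do not give the share with a slow rate, low pressure or AV block, so the number affected cannot be derived.

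**What withholding would cost the trial.**

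1. A patient withheld for a slow rate, say below 55 bpm, is already under the 65 bpm target and the 60 bpm top-up trigger. That patient also falls within the single-rotation range (below 75 bpm), so there is no reason to expect an inconclusive scan.
2. A patient withheld for pressure or AV block may have a faster rate. The scan protocol already provides for this: images are acquired "by two rotations at a heart rate of 75 to 100 bpm, and by three rotations at a heart rate above 100 bpm".
3. Planned evaluable patients are 300 × (1 − 0.18) = 246. Each scan actually lost is therefore 1/246 = 0.4% of the evaluable sample. The 18% already includes about 8% inconclusive scans (300 × 0.08 = 24).

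**The case against.** The strongest reply is that the text should be read sensibly. A clinician reviews an ECG, rate and pressure before a rate-lowering drug in order to decide whether to give it. The stated purpose is rate control, and a patient at 50 bpm needs none. Sites must have comprehensive cardiac CT experience and receive vendor-specific scan protocols. The main trial's eligibility rules may also remove some of these patients. Neither the main protocol nor the vendor protocols were supplied.

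Part of this stands. The review and the dose scaling are real safeguards, and some sites would withhold. The documents do not support an inference that unsafe patients will in fact be dosed or that anyone has been harmed. But the gap is more than silence: the requirement is stated for all patients, so a site that withholds departs from the plan. The plan also asks each site whether rate control is part of its routine, so it does not assume that it is. Eligibility is settled at randomization, and the scan comes about 90 days later.

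A reader might go further in three ways that the documents do not support:

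- **Non-serious scan-day reactions go unrecorded.** Footnote (j) in Section 1 restricts reporting to SAEs and to AEs that permanently stop study medication. Section 6.4, however, refers to the main protocol for AE reporting, and serious reactions remain reportable. Wider recording would be a preference about a scope set elsewhere.
- **The i.v. dose has no ceiling.** None is printed here, but a site or vendor protocol may set one.
- **The 60 bpm trigger contradicts the 65 bpm target.** It is stricter than the target, not inconsistent with it.

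**Conclusion.** The point holds as a gap in the written rule: pre-treatment is compulsory for every scanned patient, and neither dose scaling nor the listed contraindications lead to no drug. The rule covers about 270 patients on the plan's own attrition assumption. How many would have a reason to go untreated is unknown, and harm is not estimated.

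This is a participant-safety improvement. It does not affect the sample size or the primary analysis. A reader might suspect bias between arms or distorted leaflet grading; nothing in the documents supports that, since the rule is the same in both arms and the scan readers are blinded to treatment. The conclusion rests on this document alone, because a withhold rule may exist in protocols not supplied. Even then, the universal wording in Section 14 would conflict with it and should be amended.

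**What to change.** 1. **Technical requirements, patient preparation.** Keep pre-treatment as the default and add: *unless a withhold criterion in the scan protocol is met; the patient is then scanned without pre-treatment.*
2. **Scan protocol.** Add a withhold rule for metoprolol and ivabradine, oral and i.v. For example: resting rate below 55 bpm, systolic pressure below 100 mmHg, or second- or third-degree AV block without a pacemaker. These values are proposals, not taken from the documents, and the investigators should set them. Require pressure and ECG to be re-checked before any i.v. dose.
3. **Flag the scans** done without pre-treatment so that the core lab can describe them. The plan already states that "heart rate and blood pressure during the scan should be recorded", so the context is available.

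**Cost.** A few sentences in Section 14 and one flag per scan, with no extra visits, scans or patients. A few scans lose the standardised conditions that the plan wants. A patient withheld at a faster rate may need more gantry rotations and possibly more radiation, since Section 12 says dose depends partly on heart rate. Patients withheld for a slow rate already meet the target, so the loss of evaluable scans should be very small.
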